**Inclusion/Exclusion Criteria:** Once potentially eligible Veterans are identified and PCPs have granted permission to recruit, we will contact Veterans to identify those who meet study inclusion/exclusion criteria. Potential participants will be told that we are conducting a study to learn how Veterans can help other Veterans with chronic pain management, and that they will be randomly assigned either to the Veteran peer coach group or to the group receiving a pain self-management class. Eligible patients must 1) have musculoskeletal pain in the low back, cervical spine, or extremities (hip, knee, or shoulder) for  $\geq 3$  months; 2) have at least moderate pain severity, defined by pain  $\geq 5$  on a 0 (no pain) to 10 (worst pain imaginable) scale; and 3) indicate willingness to engage in phone or in-person contact on a regular basis with another Veteran. We have identified approximately 26,000 unique outpatients who meet criteria 1 and 2. Patients will be excluded if the electronic medical record indicates a diagnosis of a psychotic disorder (e.g., ICD-9 codes 295-295.9 for schizophrenia), current substance dependence (e.g., ICD-9 codes 304-304.9), severe medical conditions precluding participation (e.g., NY Heart Association Class III or IV heart failure, ICD-9 codes 428-428.9), or if the eligibility screener given to prospective participants reveals active suicidal ideation, severe hearing or speech impairment, or pending surgery for a musculoskeletal condition (e.g., back surgery).

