### **Control Arm**

Veterans will be randomized to either the peer coaching arm or a control group consisting of a 2-hour class in pain "basics" and pain self-management. In this class, topics listed in Part 1 (Self-Management Knowledge) of Table 1 will be reviewed (e.g., chronic pain basics, relaxation skills, activity pacing), and Veterans will be given a set of pamphlets related to pain self-management. [name] will lead the control group class; she has taught similar classes in other studies. Control participants will complete baseline assessments just prior to the class, to help encourage class attendance. (They receive compensation for assessments, see D3). We estimate offering one class per month during the study, with more offered as needed during heavier recruitment periods. To maximize attendance, some classes will be offered in the evening.

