### **Data Collection Protocol for Primary and Secondary Measures (Aims 1 and 2)**

Assessments will be given at baseline, 6 and 9 months. Participants (intervention and control) will receive \$30 per assessment. We will administer the same measures to peer coaches and Veterans, because research suggests peer coaches also benefit from peer interventions. Moreover, we want to determine whether the peers experience any negative effects related to their participation.

After obtaining informed consent, a research assistant will administer a baseline assessment to gather socio-demographic data, review the Veteran's history with an emphasis on previous and current pain treatments, and administer measures of primary and secondary outcomes. These assessments will take approximately 30 minutes each.

**Aim 1 (Primary Outcome): To compare 6- and 9-month effects of peer-supported chronic pain self-management versus controls on overall pain.** Overall pain will be measured with the Brief Pain Inventory (BPI) total score. The BPI was developed to assess the severity of pain and the impact of pain on daily functioning, and has been validated in primary care studies. The BPI is the average of two scores: pain intensity and pain interference. The pain intensity score is an average of 4 ratings of 0 (no pain) to 10 (pain as bad as you can imagine) for current, least, worst, and average pain in the past week. The BPI pain interference score averages seven ratings, 0 (does not interfere) to 10 (interferes completely), of interference with general activity, mood, walking ability, normal work, relations with other people, sleep, and enjoyment of life. The BPI total score will be used as the primary outcome measure because BPI total has been shown to be highly responsive to change in clinical trials. The BPI has been shown to have strong internal consistency in its original validation study (Cronbach's  $\alpha = 0.77$ ), the SCAMP study ( $\alpha = .83$ ), and IMPPRESS ( $\alpha = .88$ ); and the BPI assesses the two most important domains—severity and interference—recommended for pain studies.

**Aim 2 (Secondary Outcome Measures): To compare 6- and 9-month effects of peer-supported chronic pain self-management versus controls on self-efficacy, pain coping,**

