**Data Analysis for Aim 1.** We will summarize total BPI score at each time point (baseline, 6, and 9 months) for both study arms. To compare the primary outcome of total BPI score at each time point relative to baseline between two treatment arms, we will use a linear mixed-effects model fit to all time points. This model will allow us to compare the change in BPI from baseline to 6 months (primary endpoint) between treatment groups, while accounting for the correlation of measurements from the same Veteran/peer coach and adjusting for confounding factors. Fixed effects in the model will include an indicator for treatment group, time (baseline, 6, and 9 months.), treatment group by time interaction, and covariates found to differ significantly between treatment and control arm. Random effects will include a random patient-specific intercept and a random effect for peer coach within the treatment arm only. Additionally, the variance may be allowed to differ between treatment and control arms. Because this is a randomized trial design we do not expect covariates to significantly differ between the two groups. However, if there are statistically significant differences, these covariates will be included in the model. The linear mixed model for subject  $i$  in therapy group  $j$  at time  $k$  is

$$y_{ijk} = \beta_{10} + b_i + x_{ijk}'\beta + \gamma_{11}t_{ij1} + \gamma_{12}t_{ij2} + (1 - I_{ijk})r_{ijk} + (\beta_{20} + b_i + \gamma_{21}t_{ij1} + \gamma_{22}t_{ij2} + u_j + e_{ijk})I_{ijk}$$

where  $I_{ijk}$  is an indicator if patient is assigned to the treatment group,  $x_{ijk}$  is a vector of fixed covariates,  $t_{ij1}$  is an indicator for the 6-month time point,  $t_{ij2}$  is the indicator for the 9-month time point,  $b_i \sim N(0, \varepsilon^2)$  are patient-specific intercepts,  $\mu_j \sim N(0, \sigma_j^2)$  is the random effect due to peer coach  $j$ ,  $e_{ijk} \sim N(0, \sigma_T^2)$  and  $r_{ijk} \sim N(0, \sigma_C^2)$  are the residual errors for each treatment group. All analyses will include checking of assumptions and model fit. Our statistical model, which accounts for nesting of Veterans within peer coaches, will allow us to calculate the intra-class

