correlation (ICC) in the treatment group to evaluate whether there are substantial variations among peer coaches. In secondary analyses, we will also look at the BPI subscales of pain intensity and interference separately, using a similar mixed-model approach and adjusting for multiple comparisons using the Šidák method to maintain the overall confidence at 95% and to adjust for multiple comparisons. To determine if fidelity moderates patient outcomes, we will include the peer coach fidelity score by treatment group interaction and the interaction (fidelity score by time by treatment group) for the 9-month time point in the model above.

**Data Analysis for Aim 2.** Secondary measures of self-efficacy, pain coping, patient activation, social support, and health-related quality of life are continuous measures; thus the linear mixed-effects model described above will also be appropriate to analyze these measures. If a linear mixed model does not seem appropriate for a given scale, then a generalized linear mixed-effects model will be used. Since there will be a number of secondary outcomes, we will use the Šidák method. Health care utilization (number of ED visits, hospitalizations, outpatient visits, telephone visits, and analgesic prescriptions, including opioids) over the 9-month intervention will be analyzed using a generalized linear mixed model, assuming the counts follow a Poisson or negative binomial distribution. Explanatory variables in the model will include treatment indicator and, if necessary, a random effect for peer coach within the treatment group only. Covariates that significantly differ between groups will be included. If counts include a high proportion of zeros, a zero-inflated count model may be required.

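### The primary model gives baseline BPI its own arm effect, so the 6-month contrast is an unadjusted change-score difference and may leave available precision unused

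*Combined protocol and SAP*

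**What the plan says.** Data Analysis for Aim 1 fits one linear mixed model to BPI total at baseline, 6 and 9 months: "Fixed effects in the model will include an indicator for treatment group, time (baseline, 6, and 9 months.), treatment group by time interaction". In the printed equation β20 is an arm difference at baseline and γ21 is the 6-month contrast. The random effects are a patient intercept and "a random effect for peer coach within the treatment arm only", and neither varies with time. Baseline BPI is not named as a covariate, and baseline means are not constrained to be equal.

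Other covariates enter only if they are "covariates found to differ significantly between treatment and control arm". The continuous Aim 2 measures reuse this model: "thus the linear mixed-effects model described above will also be appropriate to analyze these measures". The utilization counts have a model with no baseline row, and the same rule applies: "Covariates that significantly differ between groups will be included".

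Three other passages bear on the point:
- Eligible Veterans must "have at least moderate pain severity" (Recruitment of Veterans), which may narrow the spread of baseline BPI.
- Under Control Arm: "Control participants will complete baseline assessments just prior to the class, to help encourage class attendance".
- Under Data Collection Protocol: "After obtaining informed consent, a research assistant will administer a baseline assessment to gather socio-demographic data". Its order relative to randomization is not stated.

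**The concern.** Randomization makes the true baseline means equal, but this model estimates a separate baseline mean for each arm. The 6-month contrast then subtracts the whole chance difference at baseline, when the best use of baseline subtracts only the predictable part. The loss is in precision, for the primary outcome and for every continuous Aim 2 measure.

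The covariate rule does not repair this. A time-constant covariate entered as a main effect cancels from the arm-by-time term when data are complete, even if that covariate is baseline BPI. In the utilization models nothing cancels, so the adjustment set, and hence the rate ratio, depends on which covariates happen to differ between arms.

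**Working it through.** **The plan's own figure.** Sample Size Determination states 80% power for an effect of .4, two-sided .05, 102 treated Veterans (3 per coach, ICC .3) and 80 controls. With a design effect in the treated arm only, the variance is (1 + 2 × .3)/102 + 1/80 = .02819. Power is Φ(.4/√.02819 − 1.96) = 66.4%. Without clustering it is 76.4%. The stated 80% does not reproduce; that is a separate matter, but it shows that precision is not in surplus.

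**What γ21 estimates.** Patient and coach intercepts are constant over time and arm-by-time means are saturated, so both intercepts cancel from within-patient change. A generalized least squares fit to simulated complete data, with unequal coach sizes and unequal arm variances, gave −0.911742 with a covariate and −0.208485 without. Each matched the raw change-score difference to at least 12 decimals. With about 15% of follow-up missing, the two differed (−0.288 against −0.335).

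**Patient-level precision.** Let k = SD_baseline/SD_6month, with the 6-month SD set to 1. The change-score variance is c = 1 + k² − 2rk and the adjusted variance is 1 − r². The difference is (k − r)², which is never negative and is zero only when k = r, that is, SD_baseline = r × SD_6month.

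**Assumptions for power.** Effect .4 in 6-month SDs; 102/80; 3 per coach; coach variance .3; complete data; slope b = r/k; power = Φ(.4/√v − 1.96).

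*Case A: coach effect constant over time, as the equation writes it.*
- Change: v = c(1/102 + 1/80)
- Adjusted: v = [1 − r² + .6(1 − b)²]/102 + (1 − r²)/80

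Example, k = 1, r = .5: change v = 1 × .02230 = .02230, power 76.4%. Adjusted v = (.75 + .15)/102 + .75/80 = .01820, power 84.3%. Variance falls 18.4%.

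*Case B: coach variance arises only after baseline, with a correct standard error.*
- Change: v = (c + .6)/102 + c/80
- Adjusted: v = (1 − r² + .6)/102 + (1 − r²)/80

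Power (%), change score to adjusted:

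| k | r | Case A | Case B |
|---|---|---|---|
| 1 | .4 | 68.6 to 79.1 | 60.0 to 72.2 |
| 1 | .5 | 76.4 to 84.3 | 66.4 to 75.8 |
| 1 | .6 | 85.0 to 90.0 | 73.8 to 80.4 |
| 1 | .7 | 93.3 to 95.6 | 82.2 to 86.1 |
| 1 | .8 | 98.9 to 99.3 | 90.8 to 92.4 |
| .8 | .4 | 76.4 to 80.3 | 66.4 to 72.2 |
| .8 | .5 | 83.2 to 85.5 | 72.2 to 75.8 |
| .8 | .6 | 90.1 to 91.1 | 78.7 to 80.4 |
| .7 | .4 | 79.3 to 81.1 | 68.8 to 72.2 |
| .7 | .5 | 85.4 to 86.2 | 74.2 to 75.8 |
| .7 | .6 | 91.3 to 91.5 | 80.0 to 80.4 |

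Case A variance reductions at k = 1 are 22.1, 18.4, 14.7, 11.0 and 7.4% for r = .4 to .8. Constraining baseline means instead gives 79.9, 84.9 and 90.4% at r = .4, .5 and .6.

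**Simulation of Case A** (k = 1, 3,000 runs per cell; the written three-time test against a 6-month model with baseline covariate and coach random effect): power .695/.747/.851 to .778/.837/.896 at r = .4/.5/.6. Null rejection was .046–.053 for the written test and .050–.054 adjusted.

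**Covariate rule.** The plan gives no significance threshold, so .05 is assumed. It names nine candidates: seven sociodemographics, depression and anxiety. If they are independent, the chance that at least one enters is 1 − .95⁹ = 37%. At an assumed common correlation of .2 or .4 it is 35% or 30%. No covariate-utilization association is given, so the shift in the rate ratio cannot be sized.

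**The case against.** The plan is consistent with itself: it powers and tests a difference in change, and that is a valid estimator. The gain is unknown and may be nil. It is exactly zero at k = r (for instance both .8 or both .7), and the entry criterion pushes k downwards. The larger figures come from equal SDs with r between .4 and .6. All of this stands, and it limits how much weight the point can carry.

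The unit of the .4 effect is also unstated. In change-score SDs (Case A, k = 1), change-score power is 76.4% at every r, and adjusted power is 85.9, 84.3, 82.6, 81.1 and 79.5% at r = .4 to .8. Absolute powers move with this choice; the percentage variance reductions do not.

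Neither coach case is a clean comparison. Case A lets coaches affect BPI before coaching starts. Case B is more plausible, but the written test there omits the .6/102 term from its standard error. At k = 1 it rejects 67.0, 73.9 and 81.5% of the time for r = .4, .5 and .6, so at r = .6 it exceeds the adjusted 80.4%. It does so with null rejection of 7.6, 8.1 and 8.9%. That is a separate defect, and baseline adjustment does not cure it.

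Finally, Missing Data anticipates 10–15% attrition, so the exact equivalence becomes approximate, and no gain under missing data has been calculated. The covariate rule affects only secondary utilization results and adds nothing to the primary point.

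**Conclusion.** The point holds as a loss of efficiency, not a bias. With complete data the planned primary contrast is the unadjusted change-score difference, and nothing elsewhere in the plan brings baseline BPI into use. Over r = .4 to .8 and SD ratios .7 to 1, the gain in power from adjustment runs from zero to about 12 points. It is 5 to 12 points at equal SDs with r = .4 to .6, and at most 6 points at a ratio of .8. These figures rest on assumed r, SD ratio, effect unit and coach variance structure, and on complete data. Both estimators are unbiased only if baseline BPI is unaffected by allocation. The change is worth making because it is cheap, with medium confidence in how much it will yield. The data-driven covariate set for utilization is a smaller, secondary weakness.

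**What to change.** First confirm that baseline is completed before allocation is known, in both arms. Control Arm suggests that controls may be assessed after assignment, and the data collection section does not settle the order. If that is so, it is a procedural question to resolve before the model is changed, because both options below depend on it.

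Then, for BPI and the continuous Aim 2 outcomes, do one of the following, keeping the coach random effect:
- model the 6- and 9-month values with the baseline value as a covariate; or
- keep baseline as an outcome row and constrain its mean to be equal across arms.

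In the utilization models, and in any baseline-adjusted model, replace the significance rule with a short list of prognostic covariates fixed before data lock, for example PHQ-8, GAD-7, age and sex.

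Once the order of baseline and allocation is confirmed, the cost is SAP wording only; no new data are needed.

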**Randomization.** Veterans will be randomly assigned to one of the two study arms using a table of random numbers generated by our statistician, [name]. To obtain the random treatment assignment for the 215 Veterans, five blocks of 43 Veterans will be used, and random treatment allocation will occur within each block to maintain the allocation ratio consistently across blocks. This block size is large enough to prevent investigators and research staff from guessing which treatment comes next in the sequence, while still allowing the allocation ratio to remain consistent.

**Data Analysis: Baseline Comparability.** Because of the size of this study, it is expected that randomization will produce treatment groups that are comparable and balanced. To test this assumption, we will tabulate baseline characteristics of participants and assess for potential imbalance in variables such as sociodemographics, depression, and anxiety across study arms. Additionally, descriptive statistics for baseline characteristics of peer coaches will be assessed (e.g., treatment history, including opioid use). Continuous variables will be assessed with graphical displays and summary statistics (means, standard deviation, range, etc.). Frequency distributions and percentages will be calculated for categorical data.

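### Covariates enter only when a baseline test is significant, and then only as main effects that cannot adjust the primary change contrast; the list and its form should be fixed in advance

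*Combined protocol and SAP*

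**What the plan says.** The rule appears in three places of the Combined protocol and SAP.

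- **Data Analysis for Aim 1.** The fixed effects are arm, time, arm by time, and "covariates found to differ significantly between treatment and control arm". The text adds "Because this is a randomized trial design we do not expect covariates to significantly differ between the two groups", but "if there are statistically significant differences, these covariates will be included in the model". In the equation the covariates appear once, as x'β, with no product with time.
- **Data Analysis for Aim 2.** The continuous secondary outcomes reuse the Aim 1 model. For the utilization counts: "Covariates that significantly differ between groups will be included".
- **Baseline Comparability.** The team will "assess for potential imbalance in variables such as sociodemographics, depression, and anxiety across study arms". The list of candidates is open-ended, and no test or significance level is named for the selection.

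Two further features matter. Baseline BPI is one of the modelled responses ("we will use a linear mixed-effects model fit to all time points"), and the model serves to "compare the change in BPI from baseline to 6 months (primary endpoint) between treatment groups". On the random part: "Random effects will include a random patient-specific intercept and a random effect for peer coach within the treatment arm only".

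**The concern.** After randomisation, any baseline difference between arms is due to chance. A significance test on it says nothing about whether the variable predicts pain, which is what determines whether adjustment helps. An irrelevant variable that happens to differ gets in; a strong predictor just short of significance stays out. With an open list and an unnamed test, two analysts could fit different primary models, each in line with the plan.

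The form of adjustment is a second problem. The Aim 1 text says that the model adjusts for confounding factors, but a baseline variable entered as a main effect shifts a Veteran's scores equally at all visits. The primary contrast is a within-Veteran change, so the shift drops out. At stake are precision that costs nothing to collect, and a primary model that can be written down before the arms are compared.

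**Working it through.** **1. How often the rule selects.** Assume a two-sided .05 test. Each covariate enters with probability .05, whatever its prognostic value. For K independent candidates the chance that at least one enters is 1 − .95^K: 22.6% for K = 5 and 40.1% for K = 10.

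Significance needs a standardized difference of 1.96 × √(1/n_T + 1/n_C). At the randomised 120 and 95 this is 1.96 × 0.1373 = 0.27 SD. The chance that one covariate differs by at least 0.2 SD and is still ignored is 2[1 − Φ(0.2/0.1373)] − .05 = .145 − .05 = 9.5%.

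**2. What a selected covariate does to the primary contrast.** For Veteran i with baseline covariates x_i, the modelled change is y_i6 − y_i0. The terms b_i and x_i'β occur in both scores and cancel. Because the arm main effect is free, the arm-by-time contrast is estimated from within-Veteran changes alone, so β cannot affect it with complete data. Numerical checks:

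- One simulated data set, fitted by generalised least squares with the coach effect: −0.3692, SE 0.1478, both with and without the main-effect covariate. Only a covariate-by-time term moved it.
- 300 simulated trials at 120 and 95, without a coach term in the fit: largest difference between the two estimates 0.0000 with complete data. With 15% dropout, the SD of the estimate went from 0.158 to 0.157.
- One data set with a true effect of −0.40 and an imbalanced covariate: −0.298 without it, −0.298 with a main effect, −0.413 with covariate-by-time terms.

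The utilization models have no baseline outcome term, so nothing cancels there and the rule acts directly.

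**3. The plan's own power.** Inputs from Sample Size Determination: effect .4, two-sided .05, 102 treated Veterans in 34 groups of 3, ICC .3, 80 controls, equal variances. The design effect in the treatment arm is 1 + 2(.3) = 1.6.

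SE = √(1.6/102 + 1/80) = √(0.01569 + 0.01250) = 0.1679 SD. Power = Φ(0.4/0.1679 − 1.96) = Φ(0.423) = 66.4%.

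The stated 80% is not reproduced. It would need the variance to fall to a factor of 0.72, for which the plan gives no basis. That is a separate matter; here 66.4% is the starting point because it follows from the stated inputs.

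**4. Gain from adjustment that reaches the contrast.** If the covariates together correlate r with 6-month change, the variance is multiplied by 1 − r². This assumes the same proportional reduction between and within coaches. The documents give no r, so a range is shown.

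| r (assumed) | 1 − r² | SE | Power |
|---|---|---|---|
| 0 | 1.00 | 0.1679 | 66.4% |
| .1 | .99 | 0.1670 | 66.8% |
| .2 | .96 | 0.1645 | 68.1% |
| .3 | .91 | 0.1602 | 70.5% |
| .4 | .84 | 0.1539 | 73.9% |
| .5 | .75 | 0.1454 | 78.6% |

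Starting from the nominal 80% instead, r = .2, .3, .4 and .5 give 81.6%, 83.6%, 86.4% and 89.9%.

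**5. Baseline BPI as a covariate.** If baseline and 6-month BPI correlate ρ with equal variances, a change score has variance factor 2(1 − ρ) and an analysis with the baseline score as covariate has 1 − ρ². The ratio is (1 + ρ)/2: 0.75, 0.80 and 0.85 for ρ = .5, .6 and .7. These values of ρ are also assumed.

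**The case against.** The strongest reply is that little is at risk.

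- **Baseline pain, probably the best predictor, is never at the mercy of the rule.** It is always in the model as a response, and its imbalance is subtracted in full. This stands. What remains is that full subtraction is less efficient than using the baseline score as a covariate.
- **Naming covariates in advance would not by itself help the primary contrast.** This also stands: step 2 applies equally to a pre-specified main effect. The fix must therefore say how covariates enter. The time subscript on x in the equation does not settle it, because the listed fixed effects contain no covariate-by-time term.
- **The gain may be negligible.** At r = .1 it is 0.4 percentage points. This stands too; the size depends on a correlation that the plan does not report.
- **The balance table is already descriptive.** Baseline Comparability lists graphs, summary statistics and percentages. That is so, but the Aim 1 and Aim 2 texts still make statistical significance the trigger.

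A reader might go further and infer that the rule biases the treatment estimate or inflates the false-positive rate. The documents do not support that. Randomisation keeps the unadjusted contrast unbiased on average. For a chance imbalance z, the conditional false-positive rate is 1 − Φ((1.96 − rz)/√(1 − r²)) + Φ((−1.96 − rz)/√(1 − r²)). It can exceed 5% when z is close to the cut-off, but averaged over all non-significant imbalances it is 4.6% at r = .4 and 4.3% at r = .5.

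**Conclusion.** The concern holds as a point about efficiency, chance imbalance and pre-specification. Baseline significance is the plan's only route to adjustment, and it is unrelated to prognostic value. For the BPI and the other repeated continuous outcomes, the main-effect form means that a selected covariate does almost nothing to the change contrast: nothing with complete data, very little with 15% dropout. So the covariate set depends on the data while the primary comparison stays in effect unadjusted. For the utilization counts, data-dependent selection bears directly on the result.

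The forgone power in the primary comparison lies between 0.4 points (r = .1) and 12.2 points (r = .5; 78.6 − 66.4), under a normal approximation with the stated clustering. This rests on an assumed r and on the proportional variance reduction in step 4. The 5% selection rate rests on an assumed .05 test level and, for the 40% figure, on ten independent candidates. The power range does not carry over to the counts.

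**What to change.** 1. Delete the significance trigger from the analysis texts for Aim 1 and Aim 2.
2. Name a short list of prognostic covariates already collected, for use whatever the balance table shows: for example baseline PHQ-8, GAD-7, clinic and randomisation block.
3. For the BPI and the other repeated continuous outcomes, state the form of adjustment: either covariate-by-time terms in the present model, or an analysis of follow-up scores with the baseline score as a covariate (or a baseline mean common to both arms) together with the list.
4. For the utilization counts, enter the list directly.
5. State that the balance table is descriptive and does not decide what enters any model.

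The cost is a change of SAP wording and a few degrees of freedom. With clinic grouped as RVAMC, Indy West and CBOC, and five blocks, the example list needs 1 + 1 + 2 + 4 = 8 coefficients per time point, against 102 + 80 = 182 evaluable Veterans. No new data are needed. The change should be dated before any comparison of the arms.

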### **Data Analysis**

**Sample Size Determination.** Our sample size is calculated based on estimated intervention effect on the primary outcome, the Brief Pain Inventory (BPI) total score, a continuous measure. Effect sizes for the BPI in past studies by our team have ranged from .4 to .6. Because this is our first large-scale trial with peer coaches, we will conservatively power the study based on an effect size of .4. To test for a significant difference between the BPI change from baseline to the primary 6-month endpoint between the treatment and control arm, will use a linear mixed model. With a two-sided test and a Type I error of .05, we will have 80% power to detect a .4 effect size with 102 Veterans and 34 peer coaches in the treatment group and 80 Veterans in the control arm, assuming equal variance across the two treatment arms, 3 Veterans per peer coach, and an intra-class correlation (ICC) in the treatment group of .3, which was observed in IMPRESS. (A smaller N is required in the control group because they are not nested within peer coaches.) In our prior chronic pain trials at RVAMC, retention rates were >90%. With a conservative 15% attrition rate, we will need 120 (102/.85) Veterans in the treatment arm, 40

coaches, and 95 (80/.85) Veterans in the control arm, for a total N = 215 Veterans and N = 40 coaches. We plan an intent-to-treat analysis approach.

Consistent with previous studies at RVAMC, the sample will include at least 15% minorities, reflecting the demographics of our medical center. In our SCAMP study, Blacks comprised 16% of the Veteran sample and 13% in ESCAPE. We do not plan to over-sample minorities or power sufficiently to explore racial differences in treatment response. The racial/ethnic composition of RVAMC and participating CBOCs makes exploring racial differences in treatment response impractical unless we employed special efforts to recruit minorities other than Blacks.

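### The primary model's peer-coach effect is constant over time, so it cancels from the baseline-to-6-month contrast and leaves clustering of change by coach unmodelled

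*Combined protocol and SAP*

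**What the plan says.** The paragraph Data Analysis for Aim 1 fits one linear mixed model to total BPI at baseline, 6 and 9 months, to "compare the change in BPI from baseline to 6 months (primary endpoint) between treatment groups". On the random part it says: "Random effects will include a random patient-specific intercept and a random effect for peer coach within the treatment arm only". That sentence does not say whether the coach effect changes over time. The equation does. Its treatment-arm bracket reads "\beta_{20} + b_i + \gamma_{21}t_{ij1} + \gamma_{22}t_{ij2} + u_j + e_{ijk})I_{ijk", where the indicator I is defined as assignment to the treatment group and the two t terms mark 6 and 9 months.

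The plan then relies on this structure: "Our statistical model, which accounts for nesting of Veterans within peer coaches", with the promise to report the "correlation (ICC) in the treatment group to evaluate whether there are substantial variations among peer coaches".

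The sample size paragraph concerns the same contrast: "To test for a significant difference between the BPI change from baseline to the primary 6-month endpoint between the treatment and control arm". It assumes an "intra-class correlation (ICC) in the treatment group of .3, which was observed in IMPRESS", with 3 Veterans per coach.

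On the timing of baseline, the data collection section states: "After obtaining informed consent, a research assistant will administer a baseline assessment".

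**The concern.** A coach can influence a Veteran only once coaching starts, so between-coach differences should appear at 6 and 9 months and not at baseline. A coach effect that is equal at all visits describes differences in level between coach groups. It says nothing about differences in change, which is the primary endpoint. If coaches do differ in how much their Veterans improve, the three Veterans sharing a coach have correlated changes that the model treats as independent.

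Three things are at stake: the standard error and Type I error of the primary test; the coach ICC, which would not measure what the plan wants it to measure; and the continuous Aim 2 outcomes and BPI subscales, which reuse the same or a similar model.

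There is also a slip in the equation. The patient intercept b_i is printed both outside and inside the treatment bracket, so treated Veterans carry 2b_i, or four times the control patient variance. The prose specifies one patient intercept.

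**Working it through.** **1. The plan's own figure.** Inputs from the sample size paragraph: effect .4, 102 treated (34 coaches × 3), 80 controls, ICC .3, two-sided alpha .05. The design effect is 1 + 2 × .3 = 1.6 in the treatment arm. Power = Φ(.4/√(1.6/102 + 1/80) − 1.96) = Φ(.4/.1679 − 1.96) = 66%, against the stated 80%. An unstated baseline-to-follow-up correlation (about .53 with baseline adjustment) would close the gap. That is a separate matter. What counts here is that the plan intends coach clustering to enter this contrast.

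**2. Algebra.** For a treated Veteran, leaving time-varying covariates aside:

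y(6m) − y(0) = γ11 + γ21 + e(6m) − e(0)

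Both u_j and b_i have gone. Reading I as 0 at baseline does not help: it contradicts the stated definition and leaves β20, γ21 and γ22 not separately identifiable. No other coach-by-time random effect appears in the analysis section.

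**3. Numerical check.** This is the generalised least squares standard error of the 6-month arm-by-time coefficient, with patient and residual variances of .5 each (assumed).
- 102/80, complete data: √(2 × .5 × (1/102 + 1/80)) = √.022304 = .1493 for every coach variance tried from 0 to 5, with b_i entered once or twice.
- 120/95, 15% lost after baseline: .1438 to .1440 over the same range.
- 102/80 with a post-baseline coach effect instead: .159 and .176 at coach variance .1 and .3.

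**4. Size.** Assumed: SD of change 1, all within-person correlations .5, complete data, coach differences in change with the ICC shown. The documents give no SD or between-visit correlation and do not say whether the .3 refers to level or change, so a range is shown.

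True/model variance = ((1 + 2·ICC)/102 + 1/80)/(1/102 + 1/80). Type I error = 2(1 − Φ(1.96/√ratio)).

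| Change ICC | Variance ratio | Model SE too small by | Type I error |
|---|---|---|---|
| .05 | 1.044 | 2% | 5.5% |
| .1 | 1.088 | 4% | 6.0% |
| .2 | 1.176 | 8% | 7.1% |
| .3 | 1.264 | 11% | 8.1% |

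**5. REML simulation.** 8,000 null trials per ICC, arm-specific residual variances, Monte Carlo SE about 0.25 points.

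| Change ICC | Static coach effect, b_i once | As printed (2b_i) | Coach effect on change |
|---|---|---|---|
| 0 | 5.4% | 4.4% | 5.0% |
| .05 | 6.1% | 4.8% | 5.3% |
| .1 | 6.1% | 4.9% | 5.1% |
| .2 | 7.1% | 5.7% | 5.2% |
| .3 | 7.8% | 6.6% | 5.0% |

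**6. Reported ICC.** With true change ICC .3, the median estimate is .10 (b_i once), 0 (as printed) and .30 (coach effect on change). At truth .1 the medians are .03, 0 and .10. The direction is as expected: a coach effect absent at one of three visits has an average across visits with variance (2/3)² × .3 = .13.

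**The case against.** The strongest reply accepts the algebra and disputes the harm.

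- **Selective reading.** The equation is taken literally for u_j but corrected for b_i. Taken literally throughout, the simulated Type I error is 4.8% and 4.9% at change ICC .05 and .1, so there is no inflation there. This stands as a limit on size. It does not save the model: the doubled b_i contradicts the prose, and correcting it exposes the inflation.
- **Weak evidence for a large ICC.** The .3 comes from a pilot with about 20 patients and 10 coaches and is not identified as an ICC of change. This stands, and the result is therefore conditional.
- **Small increments at low ICC.** With b_i once, simulation already gives 5.4% at ICC 0, so the excess at .05 and .1 is 0.7 points, about two Monte Carlo SEs of a difference. Clear inflation in simulation appears only at .2 and .3. This stands.
- **Cluster size.** With 15% of Veterans lost independently, the multiplier is 1 + 1.7·ICC (2 × .85 = 1.7), giving roughly 5.4% to 7.6% over the same ICCs. In the other direction, a simulation with equal coach effects at 6 and 9 months and balanced closed-form estimates gives 9.1% at ICC .3. The figures move with the covariance assumed; the direction does not.
- **Level clustering may be real.** The documents do not say how Veterans are matched to coaches, and coaches are trained in waves across nine clinics. A static effect could then capture something, but still not variation in change.
- **Model checking and fidelity terms.** The plan promises checks of assumptions and fit, and adds fidelity interactions. Neither is a coach-by-time random effect.

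**Conclusion.** The concern holds. As specified, the primary contrast does not depend on the coach variance, so the model lacks a property the plan claims for it and used in sizing the trial. That part is algebra and is certain.

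The consequence is conditional. At change ICC .05 to .3, with b_i entered once and the assumptions above, Type I error is about 5.5% to 8.1%. With the equation as printed, simulated inflation is visible only at the higher ICCs. If coaches do not differ in effect on change, there is none by this route. The coach ICC is understated as a measure of variation in change under either form. This should be fixed before analysis.

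**What to change.** Replace u_j by a treatment-arm coach effect that is zero at baseline and active afterwards (u_j × post-baseline indicator × I), or use separate 6- and 9-month coach effects. Alternatively, analyse 6-month BPI adjusted for baseline, with a coach effect in the treatment arm. Enter b_i once. Compute the ICC from the post-baseline coach variance, and state whether it and the planning value of .3 refer to level, change or baseline-adjusted score. Carry the same form to the BPI subscales and the continuous Aim 2 outcomes. An unstructured within-Veteran covariance is optional. It would guard against Veteran-level variation in change, which in one simulation (30% of the non-coach variance) raised Type I error to 6.5% even at ICC 0.

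**Cost.** One edited equation and one sentence, with the same data and software. The standard error grows by about 2% to 12%. For .4 SD of change with 102/80, power is 76% if clustering is ignored, against 75%, 73%, 70% and 66% at change ICC .05, .1, .2 and .3, using Φ(.4/SE − 1.96) with SE .1493 against .1526, .1558, .1619 and .1679. The baseline-adjusted form recovers most of this: with correlation .5 the variance is (.75 + 2c)/102 + .75/80 for coach variance c, giving about 85%, 83%, 80% and 76% at c = .05, .1, .2 and .3.

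The post-baseline form omits any clustering of level at baseline. In 2,000 simulated trials where coaches differed in level only, it kept Type I error at 4.5% to 4.7% but reported a median coach ICC of about .03 and .05 at level variance .2 and .3. The plan should therefore state how Veterans are matched to coaches.
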